6.2.2. Dose Period 1 (Day 0 and Day 2)

On Day 0/Baseline, for safety observation, Taiwanese patients are required to stay in the institution for at least 6 hours after administration of IMU-131.

IMUGENE CONFIDENTIAL

Page 2 of 2

APPENDIX 6: FLOW DIAGRAM OF PHASE 2

## List of Abbreviations

5-FU	5-fluorouracil
ADaM	Analysis Data Model
AEs	Adverse event(s)
ATC	Anatomical Therapeutic Chemical
AUC	Area Under Curve
B cell	B lymphocyte
BOR	Best overall response
CI	Confidence interval
CIV	continuous intravenous infusion
Cox-PH	Cox-proportional hazards regression model
CR	Complete Response
CRF	Case report form
CRP	C-reactive protein
CTCAE	National Cancer Institute's Common Toxicity Criteria for Adverse Events
CTS	Change in Tumor Size
DCR	Disease Control Rate
DOOR	Duration of Response
EAIR	Exposure-adjusted incidence rate
ECG	Electrocardiogram
ECOG	Eastern Cooperative Oncology Group
EoT	End of Treatment
EVAL	Evaluable Set
FAS	Full Analysis Set
GEJ	Gastroesophageal junction
GMFR	geometric mean fold rises
GMT	geometric mean titer
HER2/neu	Human epidermal growth factor receptor 2
HR	hazard ratio
ICF	Informed consent form
IDMC	Independent Data Monitoring Committee
IgG	Immunoglobulin G
IMU-131	Investigational product consisting of P467-CRM in Montanide adjuvant
ITT	Intent-to-Treat
IV	Intravenous(ly)
IxRS	Interactive Voice or Web Response System
LVEF	Left ventricular ejection fraction
MedDRA	Medical Dictionary for Regulatory Activities
NE	Not Evaluable
ORR	Objective Response Rate
OS	Overall survival
PD	Progressive Disease
PFS	Progression Free Survival
PP	Per-Protocol
PR	Partial Response
PT	preferred term

RECIST	Response Evaluation Criteria in Solid Tumors
RP2D	recommended phase 2 dose
SAP	Statistical analysis plan
SD	Stable Disease
SOC	System organ class
T cell	T lymphocyte
TEAEs	Treatment-emergent Adverse Events
ToGA	Trastuzumab for Gastric Cancer
TPP	Time to Progression
WHODD	World Health Organization Drug Dictionary

## 1. Introduction

This Statistical Analysis Plan (SAP) describes the analyses and data presentations for Imugene Limited protocol IMU.ACS.001 “HERIZON: A Phase 1b/2 Open-label Study of IMU-131 HER2/neu Peptide Vaccine Plus Standard of Care Chemotherapy with Randomization in Phase 2 in Patients with HER2/neu Overexpressing Metastatic or Advanced Adenocarcinoma of the Stomach or Gastroesophageal Junction”, which was amended on 17 Feb 2021 (Amendment No. 3). The protocol has a 2-part design: Phase 1b and Phase 2, and this SAP is specifically for the Phase 2 study. It contains definitions of analysis populations, derived variables and statistical methods for the analysis of efficacy, safety and immunogenicity.

The following analyses are planned in this study.

- Periodic safety analyses for Independent Data Monitoring Committee (IDMC) safety reviews
- The final analysis of progression free survival (PFS) after 24 evaluable PFS events have been realized
- The final analysis of overall survival (OS) after 24 deaths (at the end of study)

This SAP will only cover the secondary endpoint analysis at clinical cutoff of 24 evaluable PFS events and the primary endpoint analysis of OS at clinical cutoff of 24 OS events. The detail analyses for IDMC safety review is specified in the IDMC charter.

Throughout this SAP, the treatment group will be referred to as the IMU-131 plus chemotherapy group and chemotherapy alone group. The purpose of the SAP is to ensure the credibility of the study findings by pre-specifying the statistical approaches to any data analysis prior to database lock. This SAP will be finalized and signed prior to the clinical database lock for the final PFS analysis at 24 evaluable progression events. Any significant changes after final PFS analysis and prior to final database lock for primary endpoint OS analysis after 24 deaths will be documented in Final SAP Amendment.

All statistical analyses detailed in this plan will be conducted using SAS® 9.4 or later (SAS Institute Inc., Cary, North Carolina).

## 2. Objectives

### 2.1. Primary Objective

The primary objective of this study is to evaluate the clinical efficacy of IMU-131 plus chemotherapy compared to chemotherapy alone based on OS.

### 2.2. Secondary Objective

The secondary objectives of this study are as follows:

- To evaluate other efficacy measures of IMU-131 plus chemotherapy compared to chemotherapy alone including PFS, time to progression (TTP), disease control rate (DCR), objective response rate (ORR), duration of objective response (DOR) and change in tumor size (CTS) according to Response Evaluation Criteria In Solid Tumors version 1.1 ([RECIST 1.1](#)) for the progression evaluation of radiographic data.
- To evaluate the safety profile of IMU-131 plus chemotherapy compared to chemotherapy alone.

### 2.3. Exploratory Objective

The exploratory objective of this study is as follows:

- To evaluate humoral and cellular immunogenicity data of IMU-131 plus chemotherapy compared to chemotherapy alone including P467-specific antibodies (IgG), Her-2-specific antibodies (IgG), vaccine-specific cytokine levels and regulatory and effector T and B cells.
- To evaluate the arm-specific associations between clinical outcome, intra-tumor T cells, regulatory effector T and B cells, and serum and biochemical markers of tumor progression.
- To evaluate arm-specific associations between clinical outcome and HER2 and PD-L1 expression in tumor tissue.
- To evaluate inhibition of in-vitro tumor cell growth and intra-cellular signaling processes by Her-2-specific antibodies (IgG).

### 3. Investigational Plan

#### 3.1. Overall Study Design and Plan

[figure not shown]
This phase 1b/2 protocol for patients with HER2/neu overexpressing metastatic or advanced adenocarcinoma of the stomach or GEJ has a 2-part design: Phase 1b and Phase 2.

Phase 1b is an open-label, multicenter, single arm, dose escalation study with up to 18 enrolled to evaluate safety, tolerability and immunogenicity and to assess the Recommended Phase 2 Dose (RP2D) of IMU-131 initiated 14 days prior to the start of chemotherapy.

Phase 2 is an open-label, randomized, multicenter study to assess the clinical activity, immunogenicity, safety and tolerability of IMU-131. Phase 2 will enroll 36 patients and be conducted in the same centers as Phase 1b, with the addition of new centers as required to fulfill recruitment. Patient will be randomly assigned in a 1:1 ratio to either 'IMU-131 plus chemotherapy' or 'chemotherapy alone' groups.

The length of Phase 2 will be approximately 30 months: 22 months' recruitment and an estimated 8 months' follow-up from completion of recruitment to realization of the required number of deaths. For a representation of the timeline of events in Phase 2 see [Figure 1](#) (Timeline for Phase 2).

**Figure 1: Timeline for Phase 2**

#### Screening Period

Screening assessments or procedures will be conducted within 3 weeks prior to the start of study treatment, across at least 2 clinic visits. At the first screening visit, the patient will be asked to sign the informed consent form (ICF), the eligibility criteria will be assessed and screening for HER2/neu overexpression will be completed. All other screening procedures will be conducted at subsequent screening visits.

Patient may be re-screened under certain situations as specified in the protocol. Before re-screening, patient must sign a new ICF and will keep the same screening number. Screening procedures and test results/eligibility checks will be updated as part of re-screening.

After completing all screening assessments, patients who meet all the inclusion and none of the exclusion criteria will proceed to the treatment period.

#### Treatment Period

Patient who are determined to be eligible for the study will be randomized on the Baseline/Day 0 visit. Treatment for both groups will begin at the Baseline/Day 0 visit.

Patients in the IMU-131 plus chemotherapy group will receive vaccination of IMU-131 at Baseline/Day 0, Day 14, Day 35, Day 77, Day 140 and then every 63 days until disease progression. Patients in both the IMU-131 plus chemotherapy group and the chemotherapy alone group will receive chemotherapy starting at the Baseline/Day 0 visit and then every 21 days for a maximum of 6 cycles as clinically indicated or until disease progression, whichever occurs sooner. Chemotherapy will be consisting of:

- Cisplatin by intravenous administration at 80 mg/m^2 on the first day of each cycle and either 5-FU, 4000 mg/m^2 CIV (administered as 1000 mg/m^2/day as continuous infusion for 96 hours on days 1 to 4 of each cycle) or capecitabine for 14 days at 2000 mg/m^2/day, orally (administered as 1000 mg/m^2 twice daily morning and evening for a total of 2000 mg/m^2/day on days 1 to 14 of each cycle);
- Or oxaliplatin, by intravenous administration at 130 mg/m^2 on Day 1 of each cycle and capecitabine for 14 days at 2000 mg/m^2/day, orally (administered as 1000 mg/m^2 twice daily morning and evening for a total of 2000 mg/m^2/day on days 1 to 14 of each cycle).

Patients who withdraw from the treatment or have progressive disease will undergo the End of Treatment (EoT) assessments as planned in the [Schedule of Study Procedures](#).

### **Post-treatment Follow-up Period**

After the EoT visit, the patient will be followed up every 42 days with radiographic assessment conducted (only for patients who withdrew from study before progressive disease was confirmed), survival follow-up assessment and post-study anti-cancer treatment recorded.

### **3.2. Study Endpoints**

#### Primary Efficacy Endpoint

- OS measured from randomization to death due to any cause

#### Secondary Efficacy Endpoints

- PFS measured from randomization to date of earliest progressive disease (PD) based on blinded central review according to RECIST 1.1 criteria, or to date of death from any cause
- TTP measured from randomization to date of earliest PD based on blinded central review according to RECIST 1.1 criteria
- ORR measured from randomization as the proportion of patients achieving a best overall response of CR or PR based on blinded central review according to RECIST 1.1 criteria
- DCR measured from randomization as the proportion of patients achieving a best overall response of complete response (CR), partial response (PR) or stable disease (SD) based on blinded central review according to RECIST 1.1 criteria
- DOR measure from when earliest CR or PR is observed to PD or death due to any cause based on blinded central review according to RECIST 1.1 criteria
- Percentage CTS measured from baseline as the sum of diameters based on blinded central review according to RECIST 1.1 criteria

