	cellular signaling processes by Her-2-specific antibodies (IgG).
Endpoints	
Phase 1b study endpoints:
 
 • The safety and tolerability of IMU-131 will be evaluated by adverse events (AEs) and laboratory measurements. AEs and laboratory abnormalities will be graded by Common Terminology Criteria for Adverse Events (CTCAE) v4.03; • The recommended phase 2 dose will be evaluated by safety/tolerability and immunogenicity data for IMU-131 (P467-specific antibodies (IgG) and Her-2- specific antibodies (IgG) titers). 
Phase 1b study exploratory endpoints:
 
 • Humoral and cellular immunogenicity data will include P467-specific antibodies (IgG) and Her-2- specific antibodies (IgG) in serum samples and vaccine-specific cytokine levels as well as analysis of regulatory and effector T and B cells taken across study visits. As prediction markers of tumor progression initial evaluation (prior first vaccination) of intra-tumor T cells and regulatory cells in tumor biopsies will be performed, when these tests are available at the hospital pathology laboratory. • Radiographic data will be analyzed descriptively to explore Response Rate and provide information for sample size calculation for the Phase 2 study. 
Phase 2 Primary Efficacy Endpoint:
 
 • OS measured from randomization to death due to any cause. 
Phase 2 Secondary Efficacy Endpoints:
 
 • PFS measured from randomization to date of earliest progressive disease (PD) based on blinded central review according to RECIST 1.1 criteria, or to date of death from any cause. • TTP measured from randomization to date of earliest PD based on blinded central review according to RECIST 1.1 criteria. • DCR measured from randomization as the proportion of patients achieving a confirmed best overall response of complete response (CR), partial response (PR) or stable disease (SD) based on blinded central review according to RECIST 1.1 criteria. • ORR measured from randomization as the proportion of patients achieving a confirmed best overall response of CR or PR based on blinded central review according to RECIST 1.1 criteria. • DOR measured from when earliest CR or PR is observed to PD or death due to any cause based on blinded central review according to RECIST 1.1 criteria. • Percentage CTS measured from randomization as the sum of

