Phase 2 secondary efficacy endpoints:

- PFS measured from randomization to date of earliest progressive disease (PD) based on blinded central review according to RECIST 1.1 criteria, or to date of death from any cause.
- TTP measured from randomization to date of earliest PD based on blinded central review according to RECIST 1.1 criteria.
- DCR measured from randomization as the proportion of patients achieving a confirmed best overall response of complete response (CR), partial response (PR) or stable disease (SD) based on blinded central review according to RECIST 1.1 criteria.
- ORR measured from randomization as the proportion of patients achieving a confirmed best overall response of CR or PR based on blinded central review according to RECIST 1.1 criteria.
- DOR measured from when earliest CR or PR is observed to PD or death due to any cause based on blinded central review according to RECIST 1.1 criteria.

Investigational Product: IMU-131
Protocol Identifier: IMU.ACS.001
Protocol Version: Protocol Global Amendment #5, 27 September 2023

- Percentage CTS measured from randomization as the sum of diameters based on blinded central review according to RECIST 1.1 criteria.

Phase 2 exploratory endpoints:

- Values and changes from randomization in humoral and cellular immunogenicity data including P467-specific antibodies (IgG), Her-2-specific antibodies (IgG), vaccine-specific cytokine levels and regulatory and effector T and B cells.
- Values and changes from randomization in serum prediction markers of tumor progression.
- Values and changes from randomization in Her-2-specific antibodies (IgG) inhibition of in-vitro tumor cell growth.
- Values and changes in intra-tumor T cells and biochemical markers from pre- and post- treatment tumor biopsies.

Phase 2 Safety Endpoints:

- Incidence of treatment-emergent adverse events (TEAEs), Grade 3 / 4 / 5 TEAEs, serious adverse events (SAEs), and TEAEs leading to study treatment discontinuation.
- Incidence of treatment-emergent Grade 3 / 4 clinical laboratory abnormalities.
- Changes and shifts from randomization in clinical laboratory, vital signs, and electrocardiogram (ECG) parameters.
- Change from randomization in ECOG performance grade.
- Concomitant medication use.
- Treatment compliance.

Phase 2 Dose Escalation Primary Endpoint:

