### 8.2.3. Disease Control Rate (DCR)

The best overall response (BOR) for each patient will be derived based on blinded central review disease response assessments according to RECIST 1.1, using all the assessments from randomization until the data cutoff date or the end of study. If there is no post randomization

disease assessment, the BOR will be “No Post Randomization Assessment”; and if all the post randomization tumor responses are not evaluable, the BOR will be “Not Evaluable” (NE).

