#### **8.2.4. Objective Response Rate (ORR)**

ORR is defined as the proportion of patients with a BOR of CR or PR after randomization.

[figure not shown]

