#### **8.2.5. Duration of Objective Response (DOR)**

DOR is defined as the time from the earliest date when a tumor response of CR or PR is observed until the date of the first occurrence of disease progression or death due to any cause: Patients who don't have disease progression or have not died on or prior to the analysis cutoff date will be censored at the last adequate disease assessment date, or the earliest date of the tumor response of CR or PR observed if no disease assessment is available afterwards. See [Section 8.2.1](#) for the definition of disease progression and adequate disease assessment.

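### Phase 2 ORR and DCR require a confirmed best response in the protocol but not in the visible SAP text, so the SAP may report an ORR that is not the protocol's endpoint

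*SAP*

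**What the plan says.** **Protocol.** Section 2.2 defines the Phase 2 response rate as "ORR measured from randomization as the proportion of patients achieving a confirmed best overall response of CR or PR", judged by blinded central review under RECIST 1.1. Disease control follows the same pattern: "DCR measured from randomization as the proportion of patients achieving a confirmed best overall response of complete response (CR), partial response (PR) or stable disease". The synopsis carries the same requirement for ORR: "achieving a confirmed best overall response of CR or PR based on blinded central review".

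**SAP.** Section 3.2 gives the same two endpoints, in nearly the same sentences, without the word *confirmed*. For ORR it has "ORR measured from randomization as the proportion of patients achieving a best overall response of CR or PR", and for DCR "DCR measured from randomization as the proportion of patients achieving a best overall response of complete response (CR), partial response (PR) or stable disease (SD". Section 8.2.4 restates the first: "ORR is defined as the proportion of patients with a BOR of CR or PR after randomization".

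Section 8.2.3 derives best overall response (BOR) from central review according to RECIST 1.1, "using all the assessments from randomization until the data cutoff date or the end of study". It covers patients with no post-randomization assessment and patients whose assessments are all not evaluable. No confirmation step is visible. The SAP does use *confirmed* for progressive disease, in the downstaging rules of 8.2.1 and 8.2.2, but nowhere visible for response.

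**Duration of response.** SAP 8.2.5 says "DOR is defined as the time from the earliest date when a tumor response of CR or PR is observed". The protocol also starts DOR at the earliest CR or PR, without *confirmed*.

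**Versions.** SAP 5.0 (12 July 2022) says it follows protocol Amendment 3 (17 February 2021). The protocol under review is Amendment 5 (27 September 2023). SAP Section 13, where departures from the planned analysis would be listed, shows no text.

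**The concern.** Two governing documents define the same two named secondary endpoints differently. A programmer who follows the complete definition sentences in the SAP has no instruction to look for a second scan before counting a response. A reader of the protocol will expect that a second scan was required.

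SAP Section 12 reports ORR, DCR and DOR with the PFS analysis after 24 events. SAP 8.2.6 applies the same methods to the investigator assessments, so an unsettled rule carries into the supportive results as well. In an open-label trial, the choice between confirmed and unconfirmed response should be fixed before those results are seen, even though the central readers are blinded.

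**Working it through.** **No plan figure to reproduce.** No expected ORR or DCR, and no power or alpha for either, is visible for Phase 2. The sample-size text in protocol 10.7.2 and SAP 4.3 is largely not shown. The check is a comparison of definitions, with simple proportions for scale.

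**Inputs.**
- Phase 2 size: 36 (SAP 3.1; protocol Section 3).
- Allocation: 1:1 (SAP 3.1 and 4.4), so 36 / 2 = 18 per arm.
- Scans: Days 42, 84, 126, then every 42 days (protocol 8.4 and Table 3).

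**Step 1: apply both definitions to example patients with no other scans.**

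| Central review | ORR, visible SAP wording | ORR, protocol wording | DCR, visible SAP wording | DCR, protocol wording |
|---|---|---|---|---|
| PR Day 42, PR Day 84 | counts | counts | counts | counts |
| PR Day 42, PD Day 84 | permitted to count | does not count | counts | not determined |
| SD Day 42, PD Day 84 | does not count | does not count | counts | not determined |

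The second row separates the ORR definitions: the PR is followed by progression at the next scan, so nothing confirms it. The DCR entries are undetermined because neither document says how an unconfirmed CR or PR is classed, or what confirmed SD requires.

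**Step 2: size for ORR.** With u unconfirmed responders in an arm, ORR under the SAP wording exceeds ORR under the protocol wording by u / 18. The documents do not indicate u; 0 to 3 is an assumed range.

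| u | Shift (points) | If 9/18 respond under the SAP wording | If 6/18 respond under the SAP wording |
|---|---|---|---|
| 0 | 0 | 50.0% | 33.3% |
| 1 | 1/18 = 5.6 | 8/18 = 44.4% | 5/18 = 27.8% |
| 2 | 2/18 = 11.1 | 7/18 = 38.9% | 4/18 = 22.2% |
| 3 | 3/18 = 16.7 | 6/18 = 33.3% | 3/18 = 16.7% |

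The last two columns show the ORR under the protocol wording. Over both arms, one patient is 1/36 = 2.8 points.

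For scale, protocol Section 1.2 cites response rates of 47.3% and 34.5% with and without trastuzumab, a difference of 12.8 points. Two discordant patients in one arm here are 11.1 points.

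**Step 3: effect on the arm comparison.** The difference in ORR changes by (u in the vaccine arm − u in the control arm) / 18. Equal numbers in the two arms leave it unchanged. Nothing in the documents predicts a direction.

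**Step 4: size for DCR.** If an unconfirmed PR is reclassed as SD and that SD counts, the patient stays in DCR and the change is 0. If it is classed as not evaluable, or if confirmed SD needs a second assessment that is absent, the change is 1/18 = 5.6 points per patient affected.

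**The case against.** The strongest reply is that the difference is one word and that the visible SAP is incomplete. BOR is tied to RECIST 1.1. Section 8.2.3 is titled for DCR but shows no DCR definition, 8.2.4 has content not shown, and Section 13 is blank. A confirmation rule or a declared change could sit in any of these places, and missing text cannot be read as a gap in the plan. This stands as a limit on what can be claimed. It does not remove the conflict, because the definition sentences in SAP 3.2 and 8.2.4 are complete and differ from the protocol's.

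Several stronger readings are tempting, and the documents do not support them:

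- *One scan makes a responder under the SAP.* The wording permits this; no visible sentence states it.
- *The SAP removed a word from its source.* It cites Amendment 3, which is not available here. Only a mismatch with the current protocol can be shown.
- *DCR is inflated.* This needs a rule for confirmed SD that neither document gives.
- *SAP 8.2.5 departs from the protocol on DOR.* Both start DOR at the earliest CR or PR.
- *Response at 50 µg and at the Extension doses becomes non-comparable because of this word.* The Extension keeps *confirmed*, but it already differs by using investigator assessment in a non-randomized single arm. Protocol 10.6.2 analyzes each dose cohort separately, and this SAP covers only Phase 2.

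It is also fair to say that one rule applied to both arms under blinded central review has no shown directional effect on the comparison.

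**Conclusion.** The definition conflict is real for both ORR and DCR, and no visible text explains it. Followed as written, the SAP can report an ORR that is not the protocol's endpoint, by 5.6 points in an arm for each unconfirmed responder and 11.1 for two. The effect on DCR is undetermined and may be zero.

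This rests on three assumptions: 18 patients per arm in the denominator, a protocol meaning of *confirmed* that excludes a PR followed by PD at the next scan, and no confirmation rule in the unseen SAP text. Protocol 10.4.2 also allows analyses on smaller sets; there, each patient would weigh slightly more. ORR and DCR are secondary endpoints, and OS, PFS and TTP are unaffected. The change should be made, but it does not threaten the primary analysis.

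**What to change.** - In SAP 3.2, 8.2.3 and 8.2.4, make the protocol's confirmed BOR the main definition for ORR and DCR.
- State the rule for confirmation. CR or PR should be confirmed at a subsequent scan; the scheduled 42-day scans suffice. Neither document contains this rule, so it must be written in.
- State how an unconfirmed CR or PR is classed and what SD requires. These choices decide whether DCR changes.
- Report unconfirmed ORR and DCR as supportive.
- If unconfirmed response is what the sponsor intends, declare it as a change in SAP Section 13 and report both versions.
- In 8.2.5, state whether DOR is limited to confirmed responders. This clarifies a point open in both documents; it does not restore a protocol rule.

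The cost is SAP wording and one flag derived from scans already scheduled. The downside is that the reported ORR may be slightly lower.
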